7. AIM AND OBJECTIVES

The aim of the study is to develop and test the feasibility of an online trial of a website to increase the acceptability, uptake and adherence to long-acting reversible contraceptive (LARC) methods in young women. LARC methods include the intrauterine device (IUD), intrauterine system (IUS), subdermal implant (SDI) and depo injection.

The objectives are:

Phase 1 (completed)

1. To systematically review evidence on individual level education or decision aid interventions relating to acceptability, uptake and adherence to LARC, including underpinning theories and user and provider views.

2. To obtain the views of contraceptive service users and providers in six settings (general practice, sexual & reproductive health services, abortion services, maternity services and community pharmacies) relating to access, acceptability, uptake and adherence to LARC

3. To apply the information from objectives 1 and 2 to identify the key design issues and content for an interactive digital intervention (website) and an appropriate comparator

4. To co-develop the website with young women (through focus groups and interviews) and healthcare professionals (through an expert workshop)

Phase 2

5. To conduct a randomised pilot trial of the website in five different service settings (general practice, sexual & reproductive health service, abortion service, maternity service and community pharmacy).

6. To conduct a qualitative process evaluation with women and clinic staff, to assess the acceptability of the trial procedures, women's views of the intervention itself and implementation considerations.

7. To write a protocol for a definitive trial of an interactive digital intervention (website) to improve informed choice of contraception and the acceptability, uptake and adherence to LARC methods in young women.

8. OUTCOMES

Funder-approved Amendment to outcomes measures: (this effectively converts the secondary outcomes related to contraception into primary outcomes)

Primary Outcomes

- LARC method in use at 6 months measured by response to study outcome questionnaire
- Satisfaction with any chosen method of contraception at 6 months measured by response to study outcome questionnaire using a Likert scale 1-5. *How satisfied are you with the contraception you are using currently?*

Secondary Quantitative Outcomes

- Follow-up rate at 6 months after randomisation
- Recruitment rate measured via the trial website as the time taken to recruit (up to 80) women in each site. Recruitment is assessed by completing (in full or in part) the baseline questionnaire.
- Effectiveness of contraceptive method in use at 6 months measured by response to study outcome questionnaire and grouped as follows from least to most effective: no method; withdrawal or natural method; condoms or diaphragm; pill, patch or ring; LARC or sterilisation
- Change in method between baseline and 6 months, indicating whether any change is to a method of greater, lesser or similar effectiveness (based on grouping above)
- Pregnancy by 6 months measured at 3 months and at 6 months by response to study outcome questionnaire
- Sexually transmitted infection diagnosis by 6 months measured at 3 months and 6 months by response to study outcome questionnaire.

Health service and out-of-pocket costs for contraception and other sexual health services - measured at 3 months and at 6 months by response to study outcome questionnaire

Secondary Outcomes – qualitative

- Patient views and experience of the intervention and trial procedures, assessed through qualitative interviews at 2 weeks after randomisation with five women at each study site (total 25 interviews) (See Topic Guide). Questions to be explored include:
 - Are the online trial procedures acceptable to participants? E.g. the process of online registration and consent, the receipt of incentives, completing online questionnaires, contact and follow up by email and text
 - What are women's views of the intervention?
 - How might trial procedures be improved, to optimise retention in a full-scale trial?
- Provider views about impacts on the service and trial procedures, assessed through qualitative interviews with 15 key staff in total (3 per site), sampling those who have roles in facilitating the study in each setting (e.g. receptionists, practice managers, nurses, midwives, doctors and pharmacists) (see Topic Guide). Questions to be explored include:
 - Are recruitment procedures acceptable to staff?
 - How might recruitment procedures be improved, to optimise recruitment to a fullscale trial?
 - What are staff views on the feasibility and usefulness of a contraception decision website in each clinic setting?

9. SAMPLE SIZE and RECRUITMENT

The original target sample size of 80 participants in each of the five settings was based on estimating an expected follow-up rate at 6 months of 70% to within 10% precision (95% Cl 60% to 80%) for each setting. This sample size also provided 80% power to detect a significant difference (at the 5% level) in the follow-up rate between two settings if the true difference is 22% (e.g. 59% vs. 81%). By pooling data across settings this sample size also provides 80% power to detect a significant difference (at the 5% level) in the follow-up rate between the follow-up rate between the intervention and standard arms if the true difference is 15% (e.g. 62.5% vs. 77.5%). The expected follow-up rate is based on a previous sexual health study that recruited and followed-up the participants online (Sex Unzipped).

Funder-approved amendment to sample size:

A further 530 participants are to be recruited from one existing site, though recruited in a different way (from the central booking system). Together with the original target size this

leads to a total of 930 participants. This new total sample size is calculated to provide power to assess the effect of the intervention on the revised primary outcome which is uptake of LARC at follow-up. Specifically, assuming a follow-up rate of 70%, this sample size provides at 82% power to detect as significant (at the 5% level) an increase from 35% (control group prevalence) to 47% in LARC use due to the intervention.

The recruitment period of 6 months is based on:

- the volume of patients attending each of the study sites, which is high i.e. hundreds or dozens of women per week in four sites GP, SRH, maternity service and bpasand at least 30 women per month in the pharmacy,
- the proportion of women invited to take part in the study who accept which, given the financial incentives to take part, is expected to range from 20% to 30%.

Category	Name	Details
Sexual and Reproductive	Margaret Pyke Centre	[name]
Health Service		[name]
Abortion Service	British Pregnancy Advisory	BPAS London East. [name]
	Service	[name]
		[name].
Community Pharmacy	Green Light Pharmacy	[name]
	Shepherd's Bush	[name]
Maternity Service	Ashford & St Peter's	St Peter's Hospital,
	Hospitals NHS Foundation	[name]
	Trust	[name]
General Practice	General Practice in Camden	Clerkenwell Medical Practice
	and Islington	[name]
		[name] (to
		be confirmed)

Sites

These five clinical settings were chosen because, together, they provide contraceptive care for the great majority of women in the UK. In addition, they include services that provide care for women at highest risk of unintended pregnancy (i.e. those who attend abortion services or seek emergency contraception through community pharmacies). Development of interventions that are feasible and acceptable to women and providers in these settings therefore has the greatest potential for impact.

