10.5. Pilot trial: Statistical analysis plan

This is a pilot RCT with original primary aim of assessing the success of recruitment and retention, engagement with the intervention, and the acceptability of trial procedures to participants and clinic staff. Power calculations were performed based on data from the Sexunzipped online trial, and were described earlier.

Following the amended recruitment plan our analysis now focuses on the effect size for key outcomes including contraception choice, and satisfaction with contraceptive method.

Statistical analysis

Primary analysis will be by modified intention-to-treat – basing analysis on those who complete at least one follow-up outcome questionnaire. For each outcome listed earlier we will present the percentage of participants if the outcome is binary (e.g. use of LARC) or ordinal (e.g. effectiveness of method, satisfaction with method) and the mean if the outcome is a score (e.g. quality of life) together with a 95% confidence interval. These percentages and means will be reported separately by intervention and standard care arm, and in the case of follow-up rate and recruitment rate by setting.

To formally assess differences between arms we will use logistic regression (for binary outcomes), ordinal logistic regression (for ordinal outcomes) or linear regression (for scores) reporting adjusted intervention effect measures with 95% confidence intervals.

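### The protocol names two primary outcomes but sizes the trial for one, and gives no testing order or success rule to link them

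*Protocol*

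**What the plan says.** Section 8 (Outcomes) introduces the funder-approved change with the remark that "this effectively converts the secondary outcomes related to contraception into primary outcomes". Two items then carry the primary label. The first is given as "LARC method in use at 6 months measured by response to study outcome questionnaire". The second is the woman's own rating, on a five-point scale in the same follow-up form, of how content she is with the method she uses.

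Section 4 (Summary) gives the same pair as the main outcome measures. Section 10.5 (Pilot trial: Statistical analysis plan) calls each of them primary and gives each its own population: women in need of contraception for LARC use, and women using a method at 6 months for satisfaction.

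Section 9 (Sample size and recruitment) speaks of one outcome only. The additional recruitment "leads to a total of 930 participants", a number chosen to give power for "the revised primary outcome which is uptake of LARC at follow-up". The power statement is "82% power to detect as significant (at the 5% level) an increase from 35% (control group prevalence) to 47% in LARC use", assuming 70% follow-up. There is no power statement and no test level for satisfaction.

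On analysis, Section 10.5 says that since the amendment "our analysis now focuses on the effect size for key outcomes including contraception choice, and satisfaction with contraceptive method". It also says that differences between arms will be formally assessed by regression, "reporting adjusted intervention effect measures with 95% confidence intervals". That applies to every outcome. The protocol contains no hierarchy, no split of the 5% and no statement of whether a positive trial needs one primary outcome or both.

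**The concern.** Three sections have two primary outcomes and one section has a single primary outcome that receives the whole 5%. While the trial was a feasibility study, with follow-up and recruitment as its main measures, this would have mattered little. The amendment added 530 women to give power for a test of effect. A significant result on an outcome labelled primary is now likely to be read as evidence that the website works.

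Two primary outcomes without an order or a success rule leave that reading open. If LARC use were null and satisfaction significant, or the reverse, the report could present either as a positive primary result, and the protocol would give no ground for objecting. The chance of a false claim would then exceed the 5% used to size the trial.

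**Working it through.** **1. The protocol's own power figure.** Inputs from Section 9: 930 women, 70% follow-up, 35% against 47%, 5% level. Two-sided testing and 1:1 allocation of the additional 530 women are assumed, since neither is stated.

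- Analysed per arm: 930 × 0.70 / 2 = 325.5.
- Standard error under the null, pooled proportion 0.41: √(2 × 0.41 × 0.59 / 325.5) = 0.0386.
- Standard error under the alternative: √((0.35 × 0.65 + 0.47 × 0.53) / 325.5) = 0.0383.
- Power = Φ((0.12 − 1.96 × 0.0386) / 0.0383) ≈ Φ(1.16) = 87.7%.

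Other two-sided methods give 86.0% (continuity correction), 86.1% (Fisher exact, 325 per arm) and 88.0% (unpooled). The stated 82% is not reproduced. The difference is on the cautious side and does not bear on the present point.

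**2. Number of primary outcomes, by section.**

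| Section | Primary outcomes | Test level given |
|---|---|---|
| 4 | LARC use; satisfaction | none |
| 8 | LARC use; satisfaction | none |
| 9 | LARC use only | 5% |
| 10.5 | LARC use; satisfaction | none; 95% intervals for all outcomes |

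**3. Chance of at least one false primary claim.** Assumptions: the website affects neither outcome; each is tested at two-sided 5%; significance on either counts.

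- Independent tests: 1 − 0.95² = 0.0975, that is 9.75%.
- Upper bound whatever the correlation: 0.05 + 0.05 = 10%.
- Correlated test statistics: 1 − P(|Z₁| < 1.96 and |Z₂| < 1.96) for a bivariate normal pair. The protocol gives no correlation, so a range is shown.

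| Correlation (assumed) | Chance of at least one false claim |
|---|---|
| 0 | 9.75% |
| 0.2 | 9.64% |
| 0.3 | 9.51% |
| 0.5 | 9.07% |
| 0.7 | 8.35% |
| 0.9 | 7.04% |

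**4. Same trial, other decision rules.**

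- Both outcomes must be significant: at most 5%.
- Even split, 2.5% each: 1 − 0.975² = 4.94% if independent, never above 5%. LARC power with 325.5 per arm falls from 87.7% to 81.0%.
- Fixed order, LARC use first: if LARC use is truly unaffected, any claim needs a false positive at the first step, so at most 5%. If LARC use is truly affected, only the satisfaction claim can be false, again at most 5%. LARC power stays at 87.7%.

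**The case against.** The strongest reply is that multiplicity is usually settled in the statistical analysis plan. Section 10.11 (Data handling and analysis) foresees such a plan before database lock, and it is not at hand. This stands in part: the absence of a rule can be asserted only of the protocol. It does not remove the contradiction. How many primary outcomes there are is a matter for the protocol, which answers it in two ways, and a later plan would still have to choose between Section 9 and the other sections.

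A second reply is that this remains a pilot. Section 7 still gives feasibility as the aim and Section 10 still calls the trial a pilot. Estimating two distinct effects in different populations, each at its own level, is defensible if no combined claim is made. That too has force. But Section 10.5 also provides for formal comparison of the arms, and Section 9 justifies the enlarged sample by power to detect a significant effect.

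Two stronger readings are tempting and are not supported:

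- A reader might infer that the protocol tests both outcomes at 5% and so sets its error rate near 10%. The 5% level is written only for LARC use; for satisfaction it is inferred from the 95% intervals. No rule says that either outcome is enough, and no 5% level across both outcomes is promised.
- A reader might infer from the 82% that the 5% had been split, since 2.5% gives 81.0%. Section 9 says 5%, and other changes of input come as close: 46% in place of 47% gives 81.7%, and 60% follow-up in place of 70% gives 82.3%.

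**Conclusion.** The point holds as an internal contradiction with a conditional statistical consequence. Sections 4, 8 and 10.5 have two primary outcomes, Section 9 powers one at the full 5%, and nothing in the protocol orders them or defines success.

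The consequence rests on three assumptions: satisfaction is tested at two-sided 5%, a result on either outcome is read as a positive primary result, and the website has no effect on either. The chance of a false primary claim is then between about 7.0% (correlation 0.9) and 9.75% (independence). It is at most 5% under a rule that both must succeed, which is why the missing rule matters. This is worth correcting before the data analysis plan is agreed. It does not call the design or the sample size into question.

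**What to change.** Reconcile Sections 4, 8, 9 and 10.5 by stating one fixed testing order:

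1. LARC use at 6 months is tested first at two-sided 5%, as powered. The test is on whichever LARC effect the 90% rule in Section 10.5 makes the primary measure, so that this step is a single test.
2. Satisfaction at 6 months is tested second at two-sided 5%. It is claimed as confirmed only if the first test is significant; otherwise it is reported as an estimate with its 95% interval.

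Satisfaction can keep the primary status that the funder approved, second in order, so the amendment is not reversed. Section 9 should say that the sample size is based on the first of the two.

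The cost is a few sentences in four sections. The sample size and the power for LARC use are unchanged. The drawback is that satisfaction cannot be claimed as confirmed if LARC use is not significant. On Section 9's assumptions, with the planned LARC effect real, that would happen in 18% of trials (100 − 82, stated power) or 12.3% (100 − 87.7, recomputed). If the website truly leaves LARC use unchanged, it would happen in 95%. If that is unacceptable, an even split of the 5% avoids it, at the price of LARC power falling from 87.7% to 81.0%.

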4. SUMMARY

Reducing unintended pregnancy is a national and global priority, and improving women's choice of contraception is a vital step. There are many myths, misunderstandings and concerns about contraception, and increasingly women turn to online resources for information on healthcare.

The aim of the study is to develop and test the feasibility of an online trial of a website to increase the acceptability, uptake and adherence to long-acting reversible contraceptive (LARC) methods in young women. LARC methods include the intrauterine device (IUD), intrauterine system (IUS), subdermal implant (SDI) and depo injection.

In Phase 1 of this study (completed) we developed a self-guided website that presents recommended contraceptive options in response to women's preferences. The website will be presented on a touch-screen tablet computer in clinic waiting areas or pharmacy consulting areas.

In Phase 2 (this study), we will assess feasibility of an online trial of the contraception choice website in five sites:

An NHS sexual health service (Margaret Pyke Centre, MPC)

A local general practice

A maternity service (Ashford & St Peter's Hospitals NHS Foundation Trust)

A community pharmacy (Greenlight)

An abortion service (bpas)

Phase Two will take 15 months including:

- Conducting a randomised pilot trial across the five settings
- Conducting a qualitative process evaluation of the website, of NHS implementation issues and of research procedures
- Analysis, reporting and dissemination of study findings
- Preparation of outputs, including a protocol for a definitive RCT to increase uptake and adherence of LARC that is informed by both quantitative and qualitative findings In each setting we will recruit 80 women aged 15-30 years (40 randomised to intervention and 40 to control) and follow them up by online questionnaire at 3 and 6 months (or 2 months after delivery for post-partum women).
- *Funder-approved amendment to recruitment*. In addition to the above, we will recruit 530 more women from one site only, the Margaret Pyke Centre, via their Central (telephone) Booking System. Women requesting an appointment for

contraception will be invited to go online and enter the trial before they attend their appointment.

Data collection:

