10.4. Questionnaire Measures

Demographics:

Participants will be asked to complete a demographic questionnaire at baseline, which will assess relationship status, age, employment status, and ethnicity (See Demographic questionnaire).

Contraception questionnaire:

Participants will be asked to complete a questionnaire at baseline, and at 3 and 6 month follow-up to assess what contraceptive methods, if any, they are using currently or have used before (baseline) or since enrolling in the study (at follow-up). Participants who are currently using contraception will be asked how satisfied they are with the method. At follow-up only, participants will be asked if they have had a pregnancy and, if they have, the outcome of the pregnancy (ongoing, gave birth, miscarried, terminated, or prefer not to say). All participants are asked at baseline, 3 and 6 months, whether they have been told by a doctor or other health professional that they have a sexually transmitted infection.

Service use related to contraception and sexual health:

Participants will be asked to specify where they go to get their contraception and if they pay for it themselves.

Interaction with the intervention

In order to assess engagement with the intervention (and whether this is related to outcome), we will record website usage. The software used will record the number of times

each user visits the site, the amount of time spent on the site, the pages visited, and the amount of time spent on each page.

Methods to protect against sources of bias

Participants will provide baseline data on the tablet device before randomisation. Once eligibility for the study is established, and baseline data are collected, allocation to intervention or control group will be determined from the randomisation list, and this will not be changeable by participants or researchers. Subsequent outcome data will be collected online using an emailed weblink to the online outcome questionnaire. Data will be saved on an encrypted server, and data exported will be identifiable by study ID numbers only. Most data collection procedures are therefore automatically blind to allocation to intervention or control group, since they are automated. Sealed envelope will grant access to group allocation only to those who need to know, to for data analysis.

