The primary outcome of LARC use at 6 months will be analysed among women in need of contraception (not pregnant or currently trying to become pregnant) and the primary outcome of satisfaction with method will be analysed among women who are using a method at 6 months. The primary outcome of LARC use at 6 months will be analysed stratified by LARC use at baseline, leading to three intervention effects: the effect in baseline LARC users, the effect in baseline non-users, and the overall effect adjusted for baseline LARC use. In the event that over 90% of baseline LARC users in the control arm are using a LARC method at 6 months (or no longer need contraception) then the primary effect measure for this outcome will be the intervention effect in non-LARC users. If conversely fewer than 90% of baseline LARC users in the control arm are using a LARC method at 6 months then the primary effect measure will be the overall adjusted intervention effect. A further subgroup analysis will be conducted for both primary outcomes to assess, based on testing an interaction term, whether the effect of the intervention varies by setting.

Primary comparisons between arms will be based on multiple imputation where outcomes at 6 months are imputed based on outcomes at 3 months for those participants who completed the 3 month outcome questionnaire but failed to complete the questionnaire at 6 months.

Health Economics

The primary analysis will be a budget impact analysis of the website and contraception reporting the total costs to each payer (NHS (primary care versus secondary care), local government, private and out of pocket). This will reported as total cost of contraception and pregnancy outcomes for a range of different population sizes. The analysis will conform to the ISPOR good practice guidelines for budget impact analysis.²¹

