Costs will include the cost of contraception (NHS and out of pocket costs), including the cost of LARC implants, sexual health service use, sexual health related primary and acute care use and the cost of pregnancy related outcomes. Resource use collected as part of the trial will be costed based on published sources including Personal Social Services Research Unit (PSSRU) reference costs and British National Formulary. The cost of the website will include ongoing maintenance costs and how these might be incurred by organisations that wish to use the website in the future. This cost will be reported for a range of difference population sizes. Any costs that each setting might incur implementing the website will also be collected and reported. In addition to the budget impact analysis of total cost for each payer, we will report descriptive statistics for each cost type. We will calculate the average total health care cost of contraception per participant for the website compared to current practice at baseline and 6 months. 95% confidence intervals for each analysis will be reported based on suitable regression models and bootstrapping.

Recent work by Public Health England has also investigated the Return on Investment of contraception. This work includes 10 year costs of unintended pregnancies. Data from this tool will be used to calculate the wider 10 year costs of the contraception choices website compared to current practice for each payer.

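### As worded, the secondary outcome of pregnancy by 6 months does not exclude the pregnancy a woman already had when she enrolled at the maternity or abortion service

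*Protocol*

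**What the plan says.** Section 8 of the protocol defines the outcome as "Pregnancy by 6 months measured at 3 months and at 6 months by response to study outcome questionnaire". Section 10.4 describes the question behind it: "At follow-up only, participants will be asked if they have had a pregnancy", and those who say yes are asked for "the outcome of the pregnancy (ongoing, gave birth, miscarried, terminated, or prefer not to say". The same paragraph has sexually transmitted infection asked about at baseline as well as at both follow-ups. It describes no baseline question on pregnancy.

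Section 7 (objective 5) lists the settings as "general practice, sexual & reproductive health service, abortion service, maternity service and community pharmacy". Section 4 gives the numbers: "In each setting we will recruit 80 women aged 15-30 years (40 randomised to intervention and 40 to control". Section 10.1 admits women whose need for contraception lies in the future, so a currently pregnant woman is eligible. Section 4 times follow-up at 3 and 6 months, "or 2 months after delivery for post-partum women". Under the heading on randomisation procedures, registration is meant to happen in the waiting room before the woman is seen, except for those recruited through the booking system of the sexual health site.

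Under Health Economics (section 10.5), the budget impact analysis reports "total cost of contraception and pregnancy outcomes for a range of different population sizes". A separate 10-year projection draws on an external tool, of which the protocol says "This work includes 10 year costs of unintended pregnancies".

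**The concern.** The website can influence only pregnancies conceived after a woman has been randomised. A woman who registers in the abortion clinic's waiting room and then has the termination has had a pregnancy by any plain reading of the question. So has a woman who enrols during pregnancy and then delivers. Restricting the question to events since enrolment would not remove these cases, because the termination or birth itself comes after enrolment. The response list points the same way: apart from extreme prematurity, a birth reported by 6 months cannot come from a conception after randomisation.

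The protocol deals with pregnancy status elsewhere. Section 10.5 restricts the analysis of long-acting contraceptive use to women who need contraception, leaving out those who are pregnant or trying to conceive. The pregnancy outcome has no matching rule.

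At stake are the pregnancy percentages by arm, their formal comparison, and the pregnancy component of the cost comparison. The trial is also meant to produce a protocol for a definitive trial, which could inherit the definition.

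**Working it through.** **Inputs from the protocol.** Five settings of 80 women (section 4); 530 further women from the sexual health site and 70% follow-up (section 9).

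**Plan's own total.** 5 × 80 + 530 = 930, as section 9 states. Followed up: 930 × 0.70 = 651.

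**Women who could report an index pregnancy.**
- Both settings: 160 × 0.70 = 112, and 112/651 = 17.2%.
- Abortion service only (maternity women all enrolled after delivery): 80 × 0.70 = 56, and 56/651 = 8.6%.

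**Assumptions.** The protocol gives no rate of new pregnancy over 6 months, so r is varied. The first calculation assumes that every followed-up woman in a contributing setting reports her index pregnancy, which is a ceiling.

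**Index share** = index / (index + new). New pregnancies are r × women from the other settings (539, or 595 with one site), or r × all 651. Each cell gives the share on these two bases in that order.

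| r | Both settings (112) | Abortion service only (56) |
|---|---|---|
| 2% | 91%, 90% | 82%, 81% |
| 5% | 81%, 77% | 65%, 63% |
| 10% | 68%, 63% | 48%, 46% |

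Index pregnancies stop being the majority when new pregnancies equal them:
- Both settings: r = 112/539 = 20.8%, or 112/651 = 17.2%.
- Abortion service only: r = 56/595 = 9.4%, or 56/651 = 8.6%.

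**Relaxing full reporting.** The fraction of index women who must report theirs for a majority is (r × base)/index.
- Both settings, r = 5%: 0.05 × 539/112 = 24% to 0.05 × 651/112 = 29%.
- Both settings, r = 10%: 48% to 58%.
- Abortion service only, r = 5%: 0.05 × 595/56 = 53% to 0.05 × 651/56 = 58%.

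**Dilution.** Suppose the website halves new pregnancies among non-index women and every index pregnancy is counted. The counted proportion is (index + r × other)/651. For 4% against 2% with both settings:
- (112 + 0.04 × 539)/651 = 20.5%
- (112 + 0.02 × 539)/651 = 18.9%

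| True halving | Settings contributing | Counted proportions | Ratio |
|---|---|---|---|
| 4% to 2% | both | 20.5% v 18.9% | 0.92 |
| 4% to 2% | abortion only | 12.3% v 10.4% | 0.85 |
| 5% to 2.5% | both | 21.3% v 19.3% | 0.90 |
| 10% to 5% | both | 25.5% v 21.3% | 0.84 |

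The true ratio is 0.50 in every row.

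**Precision.** With both settings contributing, the absolute difference shrinks only to 539/651 = 83% of its true size, but the variance rises. At a 5% control rate, p(1 − p) goes from 0.05 × 0.95 = 0.048 to 0.213 × 0.787 = 0.168. Power of a two-sided 5% test is about 33% in non-index women alone (269.5 per arm) for 5% against 2.5%, and about 10% when index pregnancies are counted (325.5 per arm). For 10% against 5% it falls from about 60% to about 24%.

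**The case against.** The strongest reply is that the protocol never says index pregnancies are counted. Section 10.4 paraphrases the question; the actual form is in an appendix that is not shown and may be worded differently. This stands, and the point is therefore that the text does not exclude index pregnancies, not that it counts them.

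Second, recruiting setting and reported pregnancy outcome would already separate most cases, and section 10.11 promises an analysis plan before database lock, where such a rule could sit. This holds in part. It does not settle an ongoing pregnancy, a miscarriage or a second termination. The definition itself belongs to section 8, and an analysis plan cannot fully recover what was never asked.

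Third, the share is a ceiling. The protocol does not settle whether maternity women enrol before or after delivery: follow-up timed from delivery suggests before, while its references to post-partum women and a maternity ward leave after open. A reader might infer that most counted pregnancies will certainly be index pregnancies. The documents do not support that, since it depends on an unstated new-pregnancy rate, on the sites contributing and on reporting.

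Fourth, a reader might infer a biased comparison. Individual randomisation balances index pregnancies in expectation, and chance imbalance is reflected in the confidence interval. Even a clean comparison would have low power for effects of the size shown, and no power is claimed for this outcome. All of this stands and lowers the severity. It does not answer the loss of precision or the ratio pulled towards 1.

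**Conclusion.** The point holds as a gap in definition and data collection. Followed as written, the plan lets births and terminations from pregnancies that predate randomisation enter a secondary outcome. Up to 112 of 651 followed-up women (17%) are affected, or 56 (9%) if only the abortion service contributes. Under full reporting, index pregnancies form the majority unless new pregnancies exceed about 17% to 21%, or about 9% with one site.

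The effect is dilution of the arm comparison and added noise in pregnancy-related costs. How much noise in costs cannot be computed, because no unit costs are given. It would also go too far to say that unfiltered pregnancy counts feed the 10-year projection, since the protocol says only that the tool's data will be used. Whether to ask if a pregnancy was intended is a separate design preference and forms no part of this point.

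Severity: should-fix. The outcome is secondary, and the primary outcomes of contraceptive use and satisfaction are not called into question by this point.

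**What to change.** 1. In section 8, define the outcome as a pregnancy conceived after randomisation.
2. Record pregnancy status at baseline, or add one tick-box at follow-up asking whether the reported pregnancy is the one the woman had when she joined the study. If the unseen questionnaire already asks this, say so in section 10.4.
3. Exclude index pregnancies from the outcome and from the pregnancy-related costs in the comparison between arms.
4. For women already followed up, classify index pregnancies from setting and reported outcome: a birth at the maternity site, and the attended termination at the abortion site. Report how many cases remain unclear.

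The cost is a change of protocol wording and one question in an online form, with no change to sample size or follow-up times. The downside is fewer counted events and a wider interval around the relative effect, which would then describe only pregnancies the website could have influenced.
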